14.3 Adverse Events

Unless otherwise stated, all AE summary tables will be restricted to TEAEs, which are defined as those AEs that occurred after dosing and those existing AEs that worsened during the study. Partial dates will be imputed. For details on imputation rules, refer to Appendix A: Presentation of Data and Programming Specifications. Imputed dates are only used to determine if an AE is a TEAE: no other calculation, such as durations, will be done. If it cannot be determined whether the AE is treatment-emergent due to a partial onset date, then it will be counted as treatment-emergent. Verbatim terms in the eCRFs will be mapped to SOCs and PTs using MedDRA, version 24.1.

TEAE summaries that are displayed by SOC and PT, will be ordered by descending patient count, by SOC and PT.

Causal relationships

Causal relationship between the occurrence of an AE and the administration of the study drug is assessed by the investigator according to classification scheme: 0=not related, 1=unlikely, 2=possible and 3=probable. Probable and possible relationships will be included under the category related. All AEs must have a causal relationship assigned. In case of a missing relationship, a query will be raised in order to obtain causality assessment. In case no clarification of relationship via query is possible the missing relationship will be set to related for the analysis.

Severity

Severity grading will differ between 1=mild, 2=moderate and 3=severe. For AEs having a missing severity, the severity will not be imputed and kept as missing.

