14.3.2 Adverse Events by SOC and PT Terms

The analysis of AEs will include summary tables displaying the counts and percentages of patients experiencing AEs by SOC and PT. If a patient has more than 1 AE which codes to the same PT, the patient will be counted only once for that PT. The total number of events documented per SOC and PT will also be displayed. Summaries will be ordered by descending order of incidence of SOC and PT, within each SOC based on the frequency (proportion of patients) in the dasiglucagon group.

Frequency tables will be prepared by MedDRA terms (SOC and PT) summarizing the categories 1 to 9 as listed in Section 14.3.1.

All details relating to adverse events will also be provided in a data listing. Additional listings will be produced to display: AEs for screening failures, any AESIs, AEs leading to discontinuation of IMP, SAEs and any AEs leading to death.

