14.3 Safety Data

14.3.1 Adverse Events

**Table 14.3.1.1 Overall Summary of Adverse Events
 Safety Analysis Set**

| Adverse Event Category [n (%) m] | dasiglucagon 0.3mg (N=XX) | dasiglucagon 0.6mg (N=XX) | Total (N=XX) |
|--|------------------------------|------------------------------|-----------------|
| AEs that occurred during screening | xx (xx.x%) xx | xx (xx.x%) xx | xx (xx.x%) xx |
| Treatment-emergent adverse events (TEAEs) | xx (xx.x%) xx | xx (xx.x%) xx | xx (xx.x%) xx |
| Treatment-emergent adverse events (TEAEs) occurring within 12 hours after dosing | xx (xx.x%) xx | xx (xx.x%) xx | xx (xx.x%) xx |
| TEAEs of special interest | xx (xx.x%) xx | xx (xx.x%) xx | xx (xx.x%) xx |
| TEAEs which are other important events | xx (xx.x%) xx | xx (xx.x%) xx | xx (xx.x%) xx |
| TEAEs which are injection site reactions ^[a] | xx (xx.x%) xx | xx (xx.x%) xx | xx (xx.x%) xx |
| TEAEs which are related ^[b] to the study drug | xx (xx.x%) xx | xx (xx.x%) xx | xx (xx.x%) xx |
| Serious TEAEs | xx (xx.x%) xx | xx (xx.x%) xx | xx (xx.x%) xx |
| Serious TEAEs which are related to the study drug | xx (xx.x%) xx | xx (xx.x%) xx | xx (xx.x%) xx |
| Adverse events leading to death | xx (xx.x%) xx | xx (xx.x%) xx | xx (xx.x%) xx |

n = Number of patients; m = Number of occurrences

[a] Based on investigator assessment on the eCRF

[b] Probable and possible relationships are included under the category related. In case of missing relationship will be set to related for the analysis.

Patients reporting more than 1 event are counted only once for the patient count.

Percentages are based on the total number of patients in the safety analysis set for the given dose group.

Treatment-emergence is defined as those AEs that occurred after dosing and those existing AEs that worsened during the study.

Source: xxx

PROGRAM SOURCE: xxx.sas, DATA CUT-OFF DATE: DDMMYYYY

RUN DATE: DDMMYYYY hh:mm

Table 14.3.1.2 Treatment-Emergent Adverse Events by System Organ Class and Preferred Term
Safety Analysis Set

| System organ class Preferred term [n (%)] | dasiglucagon 0.3mg (N=XX) | dasiglucagon 0.6mg (N=XX) | Total (N=XX) |
|--|------------------------------|------------------------------|-----------------|
| Any treatment-emergent adverse events | xx (xx.x%) xx | xx (xx.x%) xx | xx (xx.x%) xx |
| System organ class 1 | xx (xx.x%) xx | xx (xx.x%) xx | xx (xx.x%) xx |
| Preferred term 1 | xx (xx.x%) xx | xx (xx.x%) xx | xx (xx.x%) xx |

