- 2) Percentages are based on total subject count (N) for each column
- 3) Sort by decreasing frequency of patients, by SOC and preferred term on the total column.
- 4) Any uncoded terms to be displayed under a SOC 'Uncoded' and then the verbatim term for the PT (in all capital letters) and to be sorted to appear at the bottom of the table

Table 14.3.1.8 Treatment-Emergent Adverse Events that are IMP Related, by System Organ Class and Preferred Term Safety Analysis Set

n = Number of patients; m = Number of events; IMP = investigational medicinal product

IMP related: Adverse events which were assessed by the investigator with a reported relationship to IMP of 'Possible' or 'Probable'.

Adverse events are coded using MedDRA version 24.1. At each level of summation (system organ class, preferred term) patients reporting more than 1 event are included only once.

Table is sorted by descending patient count, by system organ class and preferred term.

Percentages are based on the total number of patients in the safety analysis set for the given dose group.

Treatment-emergence is defined as those AEs that occurred after dosing and those existing AEs that worsened during the study.

Source: xxx

PROGRAM SOURCE: xxx.sas, DATA CUT-OFF DATE: DDMMYYYY

RUN DATE: DDMMYYYY hh:mm

Programming Note:

- 1) Repeat of table 14.3.1.2 for treatment-emergent adverse events with a reported relationship to study treatment of 'Possible' or 'Probable'.
- 2) Percentages are based on total subject count (N) for each column
- 3) Sort by decreasing frequency of patients, by SOC and preferred term on the total column.
- 4) Any uncoded terms to be displayed under a SOC 'Uncoded' and then the verbatim term for the PT (in all capital letters) and to be sorted to appear at the bottom of the table

Table 14.3.1.9 Serious Treatment-Emergent Adverse Events, by System Organ Class and Preferred Term Safety Analysis Set

n = Number of patients; m = Number of events

Adverse events are coded using MedDRA version 24.1. At each level of summation (system organ class, preferred term) patients reporting more than 1 event are included only once.

Table is sorted by descending patient count, by system organ class and preferred term.

Percentages are based on the total number of patients in the safety analysis set for the given dose group.

Treatment-emergence is defined as those AEs that occurred after dosing and those existing AEs that worsened during the study.

Source: xxx

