PROGRAM SOURCE: xxx.sas, DATA CUT-OFF DATE: DDMMYYYY

RUN DATE: DDMMYYYY hh:mm

Programming Note:

- 1) Repeat of table 14.3.1.2 for serious treatment-emergent adverse events.
- 2) Percentages are based on total subject count (N) for each column
- 3) Sort by decreasing frequency of patients, by SOC and preferred term on the total column.
- 4) Any uncoded terms to be displayed under a SOC 'Uncoded' and then the verbatim term for the PT (in all capital letters) and to be sorted to appear at the bottom of the table
- 5) Set first row in table to 'Any serious treatment-emergent adverse events' instead of 'Any treatment-emergent adverse events'.
- 6)

Table 14.3.1.10 Serious Treatment-Emergent Adverse Events that are IMP Related, by System Organ Class and Preferred Term Safety Analysis Set

n = Number of patients; m = Number of events; IMP = investigational medicinal product

IMP related: Adverse events which were assessed by the investigator with a reported relationship to IMP of 'Possible' or 'Probable'.

Adverse events are coded using MedDRA version 24.1. At each level of summation (system organ class, preferred term) patients reporting more than 1 event are included only once.

Table is sorted by descending patient count, by system organ class and preferred term.

Percentages are based on the total number of patients in the safety analysis set for the given dose group.

Treatment-emergence is defined as those AEs that occurred after dosing and those existing AEs that worsened during the study.

Source: xxx

PROGRAM SOURCE: xxx.sas, DATA CUT-OFF DATE: DDMMYYYY

RUN DATE: DDMMYYYY hh:mm

Programming Note:

- 1) Repeat of table 14.3.1.2 for serious treatment-emergent adverse events with a reported relationship to study treatment of 'Possible' or 'Probable'.
- 2) Percentages are based on total subject count (N) for each column
- 3) Sort by decreasing frequency of patients, by SOC and preferred term on the total column.
- 4) Any uncoded terms to be displayed under a SOC 'Uncoded' and then the verbatim term for the PT (in all capital letters) and to be sorted to appear at the bottom of the table

Table 14.3.1.11 Local Tolerability Assessment
Safety Analysis Set

| Treatment Group= <dasiglucagon 0.3mg (N=XX) / dasiglucagon 0.6mg (N=XX)> | | Time point | Type of Reaction | Mild | Moderate | Severe | Total |
|--|-------------------------------|------------|-------------------------|--------------|--------------|--------------|--------------|

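### Tables 14.3.1.8 and 14.3.1.10 select only reported Possible or Probable events, so they omit events whose missing causality SAP 14.3 sets to related and may not reconcile with Table 14.3.1.1

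*SAP*

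**What the plan says.** **The rule.** SAP Section 14.3 defines the related category: "Probable and possible relationships will be included under the category related". It then deals with gaps in two steps. First, "In case of a missing relationship, a query will be raised in order to obtain causality assessment". Second, if that fails, "In case no clarification of relationship via query is possible the missing relationship will be set to related for the analysis". The rule is not limited to any one table.

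**The overall summary.** In Appendix C1, footnote [b] of Table 14.3.1.1 carries the rule over: "In case of missing relationship will be set to related for the analysis".

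**The link to the by-term tables.** SAP 14.3.2 states: "Frequency tables will be prepared by MedDRA terms (SOC and PT) summarizing the categories 1 to 9 as listed in Section 14.3.1". In that list, category 7 is IMP-related TEAEs and category 9 is IMP-related serious TEAEs. Their shells are Tables 14.3.1.8 and 14.3.1.10.

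**The by-term shells.** The footnote to both tables defines the selection as "IMP related: Adverse events which were assessed by the investigator with a reported relationship to IMP of 'Possible' or 'Probable". The programming note for Table 14.3.1.8 asks for events "with a reported relationship to study treatment of 'Possible' or 'Probable", and the note for Table 14.3.1.10 reads "Repeat of table 14.3.1.2 for serious treatment-emergent adverse events with a reported relationship to study treatment of 'Possible' or 'Probable". Neither footnote and neither note mentions missing relationships.

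**The concern.** The SAP sets out one definition of a related event and its shells use two. A missing relationship set to related is neither assessed nor reported by the investigator. A programmer who follows the notes for Tables 14.3.1.8 and 14.3.1.10 literally would therefore exclude it, and the printed footnotes would present that exclusion as the definition.

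The departure is anti-conservative. It falls in the two tables that show, by term, which related and serious related events occurred, and it undoes a rule that was written to be conservative. It would also leave those tables unable to reconcile with the related rows of the overall summary. With four children per dose group, a discrepancy of one patient would be conspicuous.

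**Working it through.** The plan gives no figure to reproduce on this point. The check is a comparison of selection rules, followed by simple division.

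**Step 1: classify each causality value under each text.**

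| Causality value | SAP 14.3 and Table 14.3.1.1 | Tables 14.3.1.8 and 14.3.1.10 as written |
|---|---|---|
| Probable | related | selected |
| Possible | related | selected |
| Unlikely or not related | not related | not selected |
| Missing, resolved by query | as resolved | as resolved |
| Missing, query unsuccessful | related | **not selected** |

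The texts part only in the last row. Footnote marker [b] sits on the related-TEAE row of Table 14.3.1.1. The serious related row has no marker of its own. I assume it follows the same rule, because SAP 14.3 does not restrict the rule by row.

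**Step 2: trace where an affected event would appear.**

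- In: Table 14.3.1.1 (related row), Table 14.3.1.2 (all TEAEs) and Listing 16.2.7.1, which has a causality column.
- Also in, if serious: Table 14.3.1.9 and Listing 14.3.2.1.
- Out: Table 14.3.1.8 and, if serious, Table 14.3.1.10.

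**Step 3: size.** Inputs: 4 children planned per dose group and 8 in total (SAP Section 4). Assumption: one TEAE has unresolved missing causality.

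*Case A: the child has no other related TEAE.*

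- Table 14.3.1.1, any related: 1/4 = 25.0% in the dose group and 1/8 = 12.5% in total.
- Table 14.3.1.8 as written: 0/4 = 0% and 0/8 = 0%.
- Difference: 25.0 and 12.5 percentage points.
- If the event is serious, the same gap opens between the serious related row of Table 14.3.1.1 and Table 14.3.1.10.

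*Case B: the child also has a TEAE reported as Possible or Probable.*

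- Patients are counted once, so the number and percentage in the any-related row are the same in both tables: a difference of 0.
- The number of events is still one lower in Table 14.3.1.8. The patient counts in the affected SOC and PT rows are lower too, unless the other event falls in the same row.
- For a serious event, the serious related row agrees only if the other related TEAE is itself serious.

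*Case C: no missing causality remains after queries.* All differences are 0.

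**Step 4: after correction.** If the two shells also select missing values set to related, Table 14.3.1.8 in Case A becomes 1/4 and 1/8 and agrees with Table 14.3.1.1. No other planned figure changes.

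**The case against.** The strongest reply is that the body of the SAP already settles the matter. Section 14.3 states the rule generally, and Section 14.3.2 ties the by-term tables to the same categories. On that view the shell wording is shorthand for related that happens to leave out the imputation clause, not a second analysis rule. That is probably the intent. But the supplied text contains no statement that the body takes precedence over the shells. The restrictive wording appears in a footnote and a programming note for each of two tables, while the Table 14.3.1.1 shell does carry the clause. Even if the program followed the body, the footnotes would misdescribe the output.

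The second reply is that the trigger is remote, and this stands. SAP 14.3 requires every event to have a relationship and queries any gap. Protocol 10.3.3 obliges investigators to record their opinion on it. Under Protocol 10.1.5.1 the Trial Safety Group reviews each child's adverse events before the next child is dosed, and a serious event judged possibly or probably related pauses dosing. For serious events an unresolved gap is especially unlikely.

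A reader might infer from the mismatch that related events would vanish from the report. The documents do not support that. As traced above, the event stays in the overall summary, the all-event tables and the listings. With eight children, a reader of the listings could identify it directly. A reader might also infer that each such event shifts a dose group's related rate by 25 points. That holds only in Case A.

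**Conclusion.** The inconsistency is real. The footnotes and programming notes of Tables 14.3.1.8 and 14.3.1.10 conflict with the rule in SAP 14.3 and with the category link in SAP 14.3.2. Programmed as written, they would omit an event that the SAP classes as related.

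The consequence is limited to those two tables and their agreement with Table 14.3.1.1. At most, one affected child accounts for 25.0 points in a dose group and 12.5 points in the total column of the any-related row. This assumes four children per group, a query that fails, and no other related TEAE in that child. The expected number of such events cannot be derived from the documents and may well be zero, in which case the tables agree. This is a low-priority correction that bears on consistency of safety reporting, not on any efficacy result.

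**What to change.** In the shells for Tables 14.3.1.8 and 14.3.1.10, change both the footnote and the programming note so that the selection covers a relationship of Possible, Probable, or missing and set to related under SAP Section 14.3. Refer to the rule itself, since Section 14.3 names no derived variable. It would also help to mark any event set to related in this way in Listing 16.2.7.1, so that a reader can tell imputed from reported causality.

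The cost is two footnotes and two programming notes, plus the optional listing mark. No new data are needed, no endpoint changes, and the SAP's stated rule is left as it is.

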14.3.2 Listings of Deaths, Other Serious and Significant Adverse Events

Listing 14.3.2.1 Serious Adverse Events
 Safety Analysis Set

| Treatment | | System Organ Class/ Patient AE TE- ID # | Preferred Term/ Verbatim Term | Start Date Time (Study Day ^{b1}) / (Study Day ^{b1}) | End Date Time (Study Day ^{b1}) | Severity/ Causality | Action Taken with Treatment | Study Outcome | AESI ^{c1} / Important Type of Other Event? | Hypo. Start Important Event ^{d1} [e1]? | Plasma Glucose Value Time Source (unit) |
|-----------|------------|---|----------------------------------|---|---|------------------------|-----------------------------------|------------------|---|---|--|
| xxxx | xx Y/ N | xxxx/ xxxx/ xxxx | xxxx/ xxxx/ xxxx | YYYY-MM-DDTHH:MM (Day XX) / YYYY-MM-DDTHH:MM (Day XX) | YYYY-MM-DD (Day XX) / UNKNOWN | Mild/ Possible | Dose Reduced | Unknown | N/ Y | Infection/ Overdose/ Abuse or misuse/ Error/ Accidental exposure/ Risk of liver injury | Y HH:MM xxxxxxxx (xxx) |

Programming note:

 1) This shell continues over two pages

**Listing 14.3.2.1 Serious Adverse Events
Safety Analysis Set**

| Treatment Group - Patient ID | AE TE- # | System Organ Class/ Preferred Term/ Verbatim Term (Study Day ^(b)) | Start Date Time (Study Day ^(b)) / End Date (Study Day ^(b)) | Serious Criteria Met | | | | | |
|------------------------------------|-------------|---|---|--|---------------------------|-------|-----------------|--|---|
| | | | | Congenital Anomaly or Birth Defect | Significant Disability | Death | Hospitalization | Hospitalization or Prolongation of Life Threatening | Other Serious Important Medical Event |
| xxxx | xx | Y/ xxxx/ N xxxx/ xxxx | YYYY-MM-DDTHH:MM (XX) / YYYY-MM-DD (XX) YYYY-MM-DD (XX) / ONGOING | Y/N | Y/N | Y/N | Y/N | Y/N | Y:xxxxxx |

^(a) TEAE: Treatment-emergent AE

^(b) Study day is derived relative to the date/time of start of study drug administration.

^(c) AESI: AE of special interest

^(d) Infection=Suspicion of transmission of infectious agents via the trial product; Overdose=Overdose of the trial product; Abuse or misuse=Suspected abuse or misuse of the trial product; Error=Medication error involving the trial product; Accidental exposure=Inadvertent or accidental exposure to the trial product; Risk of liver injury=Risk of liver injury defined as ALT or AST > 3 x ULN and total bilirubin > 2 x ULN, where no alternative etiology exists;

^(e) Hypoglycemia Episode?

Adverse events are coded using MedDRA version 24.1.

PROGRAM SOURCE: xxx.sas, DATA CUT-OFF DATE: DDMMYYYY

RUN DATE: DDMMYYYY hh:mm

Programming note:

- 1) This shell continues over two pages
- 2) Sort by patient, start date and end date.

Zealand Pharma A/S
ZP4207-21052
Zealand Pharma A/S
Protocol Number: ZP4207-21052

Statistical Analysis Plan
2-Jan-25
Clinical Study Report
Page x of y

**Listing 14.3.2.2 Adverse Events Leading to Death
Safety Analysis Set**

[a] TEAE: Treatment-emergent AE
[b] Study day is derived relative to the date/time of start of study drug administration.
[c] AESI: AE of special interest
[d] Infection=Suspicion of transmission of infectious agents via the trial product; Overdose=Overdose of the trial product; Abuse or misuse=Suspected abuse or misuse of the trial product; Error=Medication error involving the trial product; Accidental exposure=Inadvertent or accidental exposure to the trial product; Risk of liver injury=Risk of liver injury defined as ALT or AST > 3 x ULN and total bilirubin > 2 x ULN, where no alternative etiology exists;
[e] Hypoglycemia Episode?
Adverse events were coded using MedDRA version 24.1.

PROGRAM SOURCE: xxx.sas, DATA CUT-OFF DATE: DDMMYYYY

RUN DATE: DDMMYYYY hh:mm

Programming note:

- 1) Repeat Listing 14.3.2.1 for records where 'Outcome' = 'Fatal'.
- 2) Sort by patient, start date and end date.

Zealand Pharma A/S

ZP4207-21052

Zealand Pharma A/S

Protocol Number: ZP4207-21052

Statistical Analysis Plan

2-Jan-25

Clinical Study Report

Page x of y

14.3.3 Narratives of Deaths, Other Serious and Certain Other Significant Adverse Events

Please refer to section 12.3.2 of the CSR

PROGRAM SOURCE: tlf-###, DATA CUT-OFF DATE: DDMMYYYY

RUN DATE: DDMMYYYY hh:mm

Programming Note: Create an empty table using the %nodata macro with that reference as message

14.3.4 Abnormal Laboratory Value Listing (Each Patient)

**Listing 14.3.4.1 Abnormal Laboratory Values
 Safety Analysis Set**

| Treatment Group - | | | | | | Change from Baseline | Normal |
|----------------------|------------|------------------|----------------------|---|-----------------------|----------------------------|--------|
| Patient ID | Category | Parameter (unit) | Visit ^(a) | Date/Time of Collection (Study Day ^(b)) | Result ^(c) | | |
| xxxx | Hematology | xxxx | Screening (BL) | YYYY-MM-DDTHH:MM (Day XX) | xxxx (L) | xxxx | xx-xx |
| | | | Follow-up | YYYY-MM-DDTHH:MM (Day XX) | xxxx (H) | | xx-xx |
| | | xxxx | Screening | | | | |

^(a) BL: Baseline Flag

^(b) Study day is derived relative to the date/time of start of study drug administration.

^(c) L: Below Normal Range, H: Above Normal Range

PROGRAM SOURCE: xxx.sas, DATA CUT-OFF DATE: DDMMYYYY

RUN DATE: DDMMYYYY hh:mm

Programming Note:

- 1) Only display Abnormal lab results (i.e. where the result does not fall within the normal range)
- 2) Sort by Patient, category (Hematology, chemistry, then coagulation), parameter and date/time
- 3) After each parameter add a blank line

14.3.5 Extent of Exposure

**Table 14.3.5.1 Hypoglycemia Induction Procedure
 Safety Analysis Set**

| | dasiglucagon 0.3mg (N=XX) | dasiglucagon 0.6mg (N=XX) | Total (N=XX) |
|--|------------------------------|------------------------------|-----------------|
| Hypoglycemia induction procedure performed? | | | |
| Yes | xx (xx.x%) | xx (xx.x%) | xx (xx.x%) |
| No | xx (xx.x%) | xx (xx.x%) | xx (xx.x%) |
| MDI User: Duration between last basal dose before the hypoglycemia procedure and time when hypoglycemia procedure was initiated (min) | | | |
| n | xx | xx | xx |
| Mean (SD) | xx.x (xx.xx) | xx.x (xx.xx) | xx.x (xx.xx) |
| Median | xx.x | xx.x | xx.x |
| Min, Max | xx, xx | xx, xx | xx, xx |
| Pump User: Duration between stop of insulin pump and time when hypoglycemia procedure was initiated (min) | | | |
| n | xx | xx | xx |
| Mean (SD) | xx.x (xx.xx) | xx.x (xx.xx) | xx.x (xx.xx) |
| Median | xx.x | xx.x | xx.x |
| Min, Max | xx, xx | xx, xx | xx, xx |
| Total amount of insulin administered to induce hypoglycemia (IU) | | | |
| n | xx | xx | xx |
| Mean (SD) | xx.x (xx.xx) | xx.x (xx.xx) | xx.x (xx.xx) |
| Median | xx.x | xx.x | xx.x |
| Min, Max | xx, xx | xx, xx | xx, xx |
| Glucose administered intravenously prior to dosing? | | | |
| Yes | xx (xx.x%) | xx (xx.x%) | xx (xx.x%) |
| No | xx (xx.x%) | xx (xx.x%) | xx (xx.x%) |
| Total amount of glucose administered (mL) | | | |
| n | xx | xx | xx |
| Mean (SD) | xx.x (xx.xx) | xx.x (xx.xx) | xx.x (xx.xx) |
| Median | xx.x | xx.x | xx.x |
| Min, Max | xx, xx | xx, xx | xx, xx |

| | dasiglucagon 0.3mg (N=XX) | dasiglucagon 0.6mg (N=XX) | Total (N=XX) |
|---|------------------------------|------------------------------|-----------------|
| Rescue IV Glucose given after dosing? | | | |
| Yes | xx (xx.x%) | xx (xx.x%) | xx (xx.x%) |
| No | xx (xx.x%) | xx (xx.x%) | xx (xx.x%) |
| Time to first IV glucose infusion (min) | | | |
| n | xx | xx | xx |
| Mean (SD) | xx.x (xx.xx) | xx.x (xx.xx) | xx.x (xx.xx) |
| Median | xx.x | xx.x | xx.x |
| Min, Max | xx, xx | xx, xx | xx, xx |

Time to first IV glucose infusion (min): Time of start of first glucose administration - Time of administration of study medication.

Source: xxx

PROGRAM SOURCE: xxx.sas, DATA CUT-OFF DATE: DDMMYYYY

RUN DATE: DDMMYYYY hh:mm

